AEs of Special Interest: Recurrent event analysis of Severe Hypoglycaemic events	Y (x4) [18]							

Endpoints	Absolute				Change from Baseline			
	Summary		Individual		Summary		Individual	
	T	F	F	L	T	F	F	L
Malignant neoplasms	Y (x10) [19]			Y				
Other significant AEs				Y				
Liver monitoring/stopping events	Y [20]			Y (x5)				
Hepatobiliary Abnormalities	Y [3]			Y				
Liver Function Tests of Potential Clinical Concern	Y							
AEs of Special Interest Overview by Subgroup	Y (x3) [21]							
AEs of Special Interest by Subgroup (Age, Sex)	Y (x4)							
Other								
eGFR [22]	Y (x2) [23]	Y			Y (x3)	Y (x2) [24]		Y [22]
eGFR (Central Lab only) [25]					Y (x2)			
BP and heart rate	Y (x2) [26]	Y (x3)			Y (x3) [27]	Y (x3)		Y [28]

NOTES :

- T = Table, F = Figure, L = Listing, Y = Yes display generated.
- Summary = Represents TFL related to any summaries (i.e. descriptive statistics) of the observed raw data.
- Individual = Represents FL related to any displays of individual subject observed raw data.

[1] ITT Population; for vital status follow-up, On-therapy, and On-treatment time periods.

[2] Frequency for On-therapy and Post-therapy combined, On-therapy, time periods (SOC and Preferred Terms, and also SOC, high level term (HLT) and Preferred Terms).

[3] Frequency for On-therapy time period.

[4] Subgroups are Age, Sex, eGFR; frequency overall and by system organ class (SOC) and HLT for the On-therapy time period.

[5] On-therapy and post-therapy combined, on-therapy, and on-therapy treatment-related.

[6] Frequency for On-therapy and Post-therapy combined, On-therapy time periods.

[7] For each type: Frequency for On-therapy and Post-therapy combined, On-therapy, time periods (SOC and Preferred Terms).

[8] Frequency for On-therapy and Post-therapy combined, On-therapy time periods (Preferred Terms).

[9] Includes any AE leading to discontinuation of IP.

[10] Includes all reported AEs/SAEs.

[11] On-therapy and Post-therapy combined, On-therapy time periods (eCRF event specific page or defined list of terms).

[12] Event-specific details recorded.

[13] Frequency overall and by SOC and Preferred Term, along with summary of characteristics, each done for On-therapy and Post-therapy combined, On-therapy time periods; also details for AESI with event-specific page for On-therapy time period.

[14] Kaplan-Meier plots for serious GI events and Investigational Product Injection Site reactions only, On-therapy time period.

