All serious adverse events, including deaths, will be recorded in the eCRF, as well as AEs leading to discontinuation of IP and AEs of special interest (AESI). MI, stroke, unstable angina requiring urgent revascularization, hospitalization for heart failure, TIA and sudden cardiac death will not be recorded as AEs or SAEs, but will instead be recorded on event-specific eCRF forms. For some AESIs (development of thyroid cancer, pancreatitis, investigational product injection site reactions, immunological reactions, severe hypoglycaemic events, atrial fibrillation/flutter, pneumonia, worsening renal function, diabetic retinopathy), additional event-specific details are also recorded in the eCRF; summaries of incidence will be provided based on these data. For the remaining AESIs, summaries of incidence will be based on defined lists of coded terms. Summaries of the AESI event-specific details will also be provided. For AESIs with incidence $\geq 1.0\%$ in either treatment group, summaries of incidence at the highest level will be provided by baseline eGFR ($\geq 90, \geq 60$ to $< 90, < 60$ ml/min/1.73m²), age ($< 65, \geq 65$ to $< 75, \geq 75$ years), and sex (female, male) subgroups. For severe hypoglycemic events, summaries of incidence will be provided by baseline HbA1c ($< 8.0\%, \geq 8.0\%$ to $< 9.0\%, \geq 9.0\%$), baseline eGFR ($\geq 90, \geq 60$ to $< 90, < 60$ ml/min/1.73m²), age ($< 65, \geq 65$ to $< 75, \geq 75$ years), and baseline sulfonylurea/insulin use (yes, no) subgroups. Data related to liver monitoring/stopping event reporting are recorded in the eCRF. Additional detail regarding definitions used to identify the AESIs are provided in Section 11.6.3.

For subjects treated with albiglutide, the frequency of immunological reaction AESIs will be summarized for the On-therapy and Post-therapy combined time period by anti-albiglutide antibody status (positive, negative, unknown) and also by IgE antibody status (positive, negative, unknown).

Frequency of malignant neoplasms (non-serious AEs or SAEs) will be summarized overall, by insulin use at baseline (yes, no), and by history of malignancy at baseline (yes, no). See Section 11.6.3 regarding definitions to be used to identify malignant neoplasms.

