- Serious GI events
- Appendicitis
- Atrial fibrillation/flutter
- Pneumonia
- Worsening renal function
- Diabetic retinopathy

For some of these AESIs (development of thyroid cancer, pancreatitis, investigational product injection site reactions, immunological reactions, severe hypoglycaemic events, atrial fibrillation/flutter, pneumonia, worsening renal function, diabetic retinopathy), event-specific details are recorded in the eCRF. Generally, the presence of these details will be used to identify these AESIs. However, for diabetic retinopathy, events will be identified if a diagnosis of diabetic retinopathy (background, pre-proliferative, or proliferative) for at least one eye is recorded on the Diabetic Eye Disease Event eCRF.

For the remaining AESIs (haematologic malignancy, pancreatic cancer, hepatic events, hepatic enzyme elevations (including GGT), serious GI events, appendicitis), these will be determined based on sets of coded terms as defined by safety review team (SRT) agreements. Per the protocol Section 6.2.3, severe hypoglycaemic events are defined as those episodes of hypoglycaemic symptoms for which the subject required assistance from another person and from which the subject recovered promptly after resuscitative actions and also including episodes of hypoglycaemic symptoms which are SAEs.

Pancreatitis events will be considered to be positively adjudicated if "Probability of Pancreatitis" = "Definite" or "Probability of Pancreatitis" = "Possible" as determined by the PAC.

Malignant Neoplasms

Malignant neoplasms are defined by SRT agreements.

Other CV Events

Following are the protocol-specified other CV events:

- Arrhythmias
- Valvulopathy

- Pulmonary hypertension
- Peripheral Arterial Thromboembolism
- Deep Venous Thrombosis/Pulmonary Embolism
- Revascularization (other than revascularizations intended for CEC adjudication)

Arrhythmias will be determined based on data recorded in the Arrhythmia eCRF form excluding events that are indicated as having electrocardiogram (ECG) result of only "Atrial flutter" and/or "Atrial Fibrillation". Revascularization (other than revascularizations intended for CEC adjudication) will be determined based on data recorded in the percutaneous coronary intervention (PCI) eCRF form and the coronary artery bypass graft (CABG) eCRF form excluding events indicated as reason = "Acute coronary syndrome".

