
Time to Event endpoints	
Metabolic Management Events	
	
qualify as an event; such cases will be identified by recording as "Renal Replacement" and also "Other, Specify" with corresponding text description.
 
 ○ New diabetes-related blindness (Diabetic Eye Disease Event eCRF form, Visual Function, "Severity of Visual Impairment"= "Able to count fingers or worse (Blindness)" and also "Does the subject have visual impairment (after best possible correction with glasses)"="Yes" and also "Is the visual impairment diabetes related"="Yes"); event date is the date of diagnosis of new or worsening diabetic retinopathy/maculopathy. ○ Procedures (Diabetic Eye Disease Event eCRF form, Treatment: "Anti-VEGF Treatment"="Yes", "Photocoagulation"="Yes", or "Vitrectomy" indicated in one or both eyes); event date is the corresponding date of treatment.

Composite Metabolic Endpoint	
	
 • The composite metabolic endpoint is defined in Section 2 of the protocol. Subjects will be defined as achieving the composite metabolic endpoint based on the following criteria: glycaemic control ($\text{HbA1c} \leq 7.0\%$ at final assessment) with no severe hypoglycaemic incidents and weight gain <5% from baseline • The final assessment is defined as the latest post-baseline assessment of both HbA1c and weight (on same date) in the corresponding time period (either overall or On-treatment). • Severe hypoglycaemic incidents will be determined by an event being recorded in the Severe Hypoglycaemic Event eCRF form with a start date that is post-baseline and is on or before the final assessment date defined above for the corresponding time period (either overall or On-treatment).

HbA1c	
	
 • For HbA1c measured in mmol/mol, values will be converted to % based on the following [Geistanger, 2008]: $\text{HbA1c (\%)} = [0.09148 * \text{HbA1c (mmol/mol)}] + 2.152$ 
In a similar manner, for HbA1c measured in %, values will be converted to mmol/mol based on solving the above equation accordingly:
 $\text{HbA1c (mmol/mol)} = [\text{HbA1c (\%)} - 2.152] / 0.09148$

Time to Event endpoints	
TIA	

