3.038	Summary of On-therapy Serious Adverse Events Leading to Permanent Discontinuation of Study Treatment by SOC and PT	Safety	SOC and PT, #/% of subjects and # of events, event density

Table No.	Title	Population	Programming note
3.039	Overview of On-therapy and Post-therapy Adverse Events of Special Interest	Safety	#/% of subjects, incidence rate (subjects/100PY) and # of events and event density (events/100PY): overall for each type of AESIs, relative risk (95% CI) - includes incidence based on CMQ/ SMQ for AESIs that do not have event-specific page, otherwise based on event-specific page only.
3.040	Overview of On-therapy Adverse Events of Special Interest	Safety	As per 8A, above.
3.041	Overview of On-therapy Adverse Events of Special Interest by Baseline eGFR (Incidence $\geq 1\%$ in Either Treatment Group)	Safety	As per 8A eGFR subgroups (<60 , ≥ 60 to <90 , ≥ 90 ml/min/1.73m ²)
3.042	Overview of On-therapy Adverse Events of Special Interest by Sex (Incidence $\geq 1\%$ in Either Treatment Group)	Safety	As per 8A.
3.043	Overview of On-therapy Adverse Events of Special Interest by Age (Incidence $\geq 1\%$ in Either Treatment Group)	Safety	As per 8A. <65 , ≥ 65 to <75 , ≥ 75 years
3.044	Summary of On-therapy and Post-therapy AESIs by Age	Safety	SOC and PT, #/% of subjects and # of events, event density

Table No.	Title	Population	Programming note
3.045	Summary of On-therapy AESIs by Age	Safety	SOC and PT, #/% of subjects and # of events, event density
3.046	Summary of On-therapy and Post-therapy AESIs by Sex	Safety	SOC and PT, #/% of subjects and # of events, event density
3.047	Summary of On-therapy AESIs by Sex	Safety	SOC and PT, #/% of subjects and # of events, event density
3.048	Overview of On-therapy and Post-therapy AESIs: Thyroid Cancer Diagnosis	Safety	
3.049	Summary of On-therapy and Post-therapy AESIs: Thyroid Cancer Diagnosis, by SOC and PT	Safety	SOC and PT, #/% of subjects and # of events, event density
3.050	Overview of On-therapy AESIs: Thyroid Cancer Diagnosis	Safety	
3.051	Summary of Investigator-reported Characteristics of On-therapy AESIs of Thyroid Cancer Diagnosis	Safety	
3.052	Summary of On-therapy AESIs: Thyroid Cancer Diagnosis, by SOC and PT	Safety	SOC and PT, #/% of subjects and # of events, event density
3.053	Overview of On-therapy and Post-therapy AESIs: Haematologic Malignancy	Safety	

Table No.	Title	Population	Programming note

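### Severe hypoglycaemia is defined to include every hypoglycaemic SAE, but is counted only when the Severe Hypoglycaemic Event page is present

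*SAP*

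**What the plan says.** SAP Section 8.2.1 splits the 15 AESIs into two groups. Nine have their own eCRF details: thyroid cancer, pancreatitis, investigational product injection site reactions, immunological reactions, severe hypoglycaemia, atrial fibrillation/flutter, pneumonia, worsening renal function and diabetic retinopathy. For these, "additional event-specific details are also recorded in the eCRF; summaries of incidence will be provided based on these data". For the other six, "For the remaining AESIs, summaries of incidence will be based on defined lists of coded terms". A note to Table 7 treats the two sources as alternatives: "eCRF event specific page or defined list of terms".

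Section 11.6.3 repeats the split for the nine: "Generally, the presence of these details will be used to identify these AESIs". The one exception it names, diabetic retinopathy, is also page-based and additionally needs a recorded diagnosis. The programming note to Table 3.039 in Section 11.15.6 is firmer, using coded terms "for AESIs that do not have event-specific page, otherwise based on event-specific page only". Table 3.040 inherits the rule through "As per 8A, above", and Tables 3.041 to 3.043 point to the same label. No listed table carries it; by position it means Table 3.039.

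Section 11.6.3 also gives the definition of severe hypoglycaemia, taken from the protocol: episodes needing another person's help with prompt recovery, "and also including episodes of hypoglycaemic symptoms which are SAEs". For the composite metabolic endpoint, Section 11.6.4 states: "Severe hypoglycaemic incidents will be determined by an event being recorded in the Severe Hypoglycaemic Event eCRF form".

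**The concern.** The second limb of the hypoglycaemia definition depends on seriousness, not on which form was filled in. The counting rule depends on the form. An episode can therefore satisfy the plan's definition, be in the database as a coded SAE, and still not be counted as severe hypoglycaemia.

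Three analyses are exposed. AESIs are a secondary safety endpoint, with relative risks and confidence intervals planned. Severe hypoglycaemia has its own recurrent-event analysis in Section 8.2.2. It is also one of the three conditions of the composite metabolic endpoint, where an uncounted event favours the subject: someone who meets the HbA1c and weight conditions would be classed as a success. The report could also disagree with itself, since the SAE tables by Preferred Term do not depend on the page.

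**Working it through.** No stated figure is at issue, so the check sets the rules side by side and then sizes the effect under assumptions.

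**Step 1. Does a hypoglycaemia SAE with no page count as severe hypoglycaemia?**

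| Place in the SAP | Basis | Counted? |
|---|---|---|
| 11.6.3, definition | Symptomatic episode that is an SAE | Yes |
| 11.6.3, identification | Page details present | No |
| 8.2.1 | Page details | No |
| 11.15.6, Table 3.039 note (3.040-3.043 by reference) | Page only | No |
| 11.6.4, composite metabolic endpoint | Form entry | No |
| 8.2.2, recurrent-event analysis | No source named | Presumably not |
| 11.15.6, Tables 3.023-3.024, SAEs by SOC and PT | Coded SAE | Shown as an SAE |

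**Step 2. Can the two records come apart?** Section 8.2.1 has all SAEs recorded in the eCRF and treats the event-specific details as additional. Section 9.2.1, on narratives, places serious hypoglycaemic episodes in the SAE set. The SAE record and the page are therefore separate entries. The SAP states no reconciliation between them, no coded-term back-up and no sensitivity count.

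**Step 3. Size, as illustration only.** Inputs: about 9,400 subjects randomised 1:1 (Section 2.3), so 9,400 / 2 = 4,700 per arm. The incidences and missing-page shares are assumptions.

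- *Counts.* At 1% incidence, 0.01 × 4,700 = 47 subjects per arm. With 2-10% of pages missing, 0.02 × 47 = 0.9 to 0.10 × 47 = 4.7, or about 1-5 subjects.
- *Composite endpoint.* Even if all 4.7 subjects met the other two conditions, 4.7 / 4,700 = 0.1 percentage point of the arm would be misclassified.
- *Relative risk.* With missing shares m_A (albiglutide) and m_P (placebo), observed RR = true RR × (1 − m_A)/(1 − m_P). Equal shares leave the RR unchanged. With true RR 1.00, 10% v 20% missing gives 0.90/0.80 = 1.12, and the reverse gives 0.80/0.90 = 0.89.
- *Precision.* SE(log RR) = √(1/a − 1/4,700 + 1/b − 1/4,700), on expected counts a and b. This is a log-normal interval, whereas Section 8.2.2 plans an exact unconditional one. For true risks of 0.6% v 0.3%, 28.2 v 14.1 events give RR 2.00 (1.06-3.79). At 10% missing in both arms, 25.4 v 12.7 give 2.00 (1.02-3.92). At 20%, 22.6 v 11.3 give 2.00 (0.98-4.08).
- *Display threshold.* An AESI with true incidence 1.1% in both arms falls to 1.1% × 0.90 = 0.99% at 10% missing. It would then drop out of the subgroup overviews, which require 1.0% in either arm (Section 8.2.1).

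**The case against.** The strongest reply is that a clinical definition paired with a data source is not an error. The definition says what qualifies, the page is where it is recorded, and nothing exempts a serious episode from the page. Section 3.2 requires database cleaning before freeze, and edit checks outside the SAP may force the page for every such SAE. This stands as a limit on size: with complete pages, nothing changes. It does not remove the mismatch, because the SAP's rule is narrower than its definition and nothing in the SAP closes the gap.

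A reader might go further and infer that all nine page-based AESIs are wrongly counted. The SAP does not support that. For pancreatitis, thyroid cancer and the rest it gives no separate definition that the page rule contradicts; there is only a capture route without a stated back-up. Nor are such events lost from the report. SAEs appear by SOC and Preferred Term, and a thyroid cancer would also be expected in the malignant neoplasm tables (3.136-3.145), which use safety review team definitions. Pancreatitis has adjudicated tables (3.119-3.123), although the SAP does not say whether a coded event without a page reaches that committee.

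A reader might also infer a large or one-directional bias. Losing one of five events in one arm moves a ratio from 1.0 to 0.8. That is a 20% one-sided loss; at 2-10% missing, the expected loss from five events is 0.1-0.5. With 5 v 5 events the approximate 95% interval is already 0.29-3.45. The trial is double-blind, and the documents offer no mechanism for unequal page completion. Page-only counting undercounts relative to page or coded term, but not necessarily relative to the truth, since a page may be completed for a non-qualifying event.

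**Conclusion.** The point holds for severe hypoglycaemia. The SAP defines these events to include all symptomatic hypoglycaemic SAEs, then counts them only when the page is present. An SAE without the page is left out of the AESI incidence and relative-risk tables and the composite metabolic endpoint. It is presumably also left out of the recurrent-event analysis, provided that analysis uses the same identification. It remains visible in the SAE tables.

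The size cannot be determined from the SAP. It is zero with complete pages and, under the assumptions above, a few subjects per arm. Incidence would be understated, while the relative risk would shift only if completion differed between arms. For thyroid cancer, pancreatitis, atrial fibrillation/flutter and pneumonia, the finding is a capture gap worth a sensitivity count, not a contradiction. The primary MACE analysis is untouched. The change should be made before unblinding.

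**What to change.** 1. In Sections 11.6.3 and 11.6.4 and the Table 3.039 note, count a severe hypoglycaemic event when the page is present or an SAE is coded to hypoglycaemia. An episode with both records counts once.
2. Use that single flag in the AESI tables, the recurrent-event analysis and the composite metabolic endpoint, and name it as the source in Section 8.2.2. Keep page-only as a sensitivity count.
3. For thyroid cancer, pancreatitis, atrial fibrillation/flutter and pneumonia, keep the page-based count as primary. Add a sensitivity count of page or coded AE/SAE term, and reconcile terms with pages before unblinding.
4. Do not apply a term union to injection site reactions: Section 2.1 specifies investigational product reactions, which a coded term alone cannot show. Do not apply one to diabetic retinopathy either, because it would bypass the diagnosis that Section 11.6.3 requires.
5. Replace the 8A label in Tables 3.040 to 3.043 with 3.039.

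The cost is some SAP wording, one analysis flag and a few term lists. The lists have to be agreed, because Section 11.6.3 refers to safety review team terms only for the six other AESIs and malignant neoplasms. A few coded events will lack the page details needed for the characteristics tables.

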11.15.7. Safety Figures

Figure No.	Title	Population	Programming note
3.01	Kaplan-Meier Plot of Time to Death (Vital Status Follow-up Time Period)	ITT	
3.02	Kaplan-Meier Plot of Time to Death (On-therapy Time Period)	ITT	
3.03	Kaplan-Meier Plot of Time to Death (On-treatment Time Period)	ITT	
3.04	Common (>=2%) On-therapy Serious Adverse Events Sorted by Relative Risk	Safety	
3.05	On-therapy Adverse Events of Special Interest Sorted by Relative Risk	Safety	
3.06	Kaplan Meier Plot of Time to First Investigational Product Injection Site Reaction (On-therapy Time Period)	Safety	
3.07	Kaplan Meier Plot of Time to First Serious GI Event (On-therapy Time Period)	Safety	
3.08	Line Graph of Mean (+/-SE) eGFR (ml/min/1.73m ²) Over Time	Safety	
3.09	Line Graph of Mean (+/-SE) Change from Baseline eGFR (ml/min/1.73m ²) Over Time	Safety	
3.10	Line Graph of Adjusted Mean (+/-SE) Change from Baseline On-treatment eGFR (ml/min/1.73m ²) Over Time	Safety	Plot adjusted means.
3.11	Line Graph of Mean (+/-SE) SBP (mmHg) Over Time	Safety	
3.12	Line Graph of Mean (+/-SE) Change from Baseline SBP (mmHg) Over Time	Safety	
3.13	Line Graph of Mean (+/-SE) DBP (mmHg) Over Time	Safety	
3.14	Line Graph of Mean (+/-SE) Change from Baseline DBP (mmHg) Over Time	Safety	

Figure No.	Title	Population	Programming note
3.15	Line Graph of Mean (+/-SE) Heart Rate (bpm) Over Time	Safety	
3.16	Line Graph of Mean (+/-SE) Change from Baseline Heart Rate (bpm) Over Time	Safety	
3.17	Scatter Plot of Maximum vs. Baseline for ALT	Safety	
3.18	Scatter Plot of Maximum Total Bilirubin versus Maximum ALT - eDISH	Safety	
3.19	Box Plot of Creatinine (umol/l) Over Time	Safety	
3.20	Box Plot of Change from Baseline Creatinine (umol/l) Over Time	Safety	

11.15.8. VEO Tables

Table No.	Title	Population	Programming note
4.01	Summary of TRIM-D Total Score (Observed Cases)	ITT	Exclude subjects not on diabetes medication at baseline.
4.02	Summary of TRIM-D Total Score (LOCF)	ITT	Exclude subjects not on diabetes medication at baseline.
4.03	Summary of MMRM Analysis of TRIM-D Total Score Change From Baseline (Observed Cases)	ITT	Exclude subjects not on diabetes medication at baseline.
4.04	Summary of TRIM-D Treatment Burden Domain Score (Observed Cases)	ITT	Exclude subjects not on diabetes medication at baseline.
4.05	Summary of TRIM-D Daily Life Domain Score (Observed Cases)	ITT	Exclude subjects not on diabetes medication at baseline.
4.06	Summary of TRIM-D Diabetes Management Domain Score (Observed Cases)	ITT	Exclude subjects not on diabetes medication at baseline.

Table No.	Title	Population	Programming note
4.07	Summary of TRIM-D Compliance Domain Score (Observed Cases)	ITT	Exclude subjects not on diabetes medication at baseline.
4.08	Summary of TRIM-D Psychological Health Domain Score (Observed Cases)	ITT	Exclude subjects not on diabetes medication at baseline.
4.09	Summary of EQ-5D VAS Score (Observed Cases)	ITT	
4.10	Summary of EQ-5D VAS Score (LOCF)	ITT	
4.11	Summary of MMRM Analysis of EQ-5D VAS score Change From Baseline (Observed Cases)	ITT	
4.12	Summary of EQ-5D Mobility Domain (Observed Cases)	ITT	
4.13	Summary of EQ-5D Self-Care Domain (Observed Cases)	ITT	
4.14	Summary of EQ-5D Usual Activities Domain (Observed Cases)	ITT	
4.15	Summary of EQ-5D Pain/Discomfort Domain (Observed Cases)	ITT	
4.16	Summary of EQ-5D Anxiety/Depression Domain (Observed Cases)	ITT	
4.17	Summary of In-patient Healthcare Resource Utilization	ITT	
4.18	Summary of Managing Diabetes Questionnaire Data	ITT	
4.19	Summary of Managing Diabetes Questionnaire Data: Question 1	ITT	
4.20	Summary of Managing Diabetes Questionnaire Data: Question 3	ITT	

